## Study Protocol and Statistical Analysis Plan

# Cryoballoon Ablation Versus Medical Therapy in Patients with Atrial Fibrillation and Heart Failure with Different Ejection Fraction Categories

### 1. Study objective

This study is to assess the effectiveness and safety of cryoballoon ablation comparing with medical therapy in patients with atrial fibrillation and heart failure with different ejection fraction categories

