### 2. Study Design

Study Type	Interventional (Clinical Trial)
Estimated Enrollment:	200 participants
Allocation:	No-Randomized
Intervention Model:	Parallel Assignment
Primary Purpose:	Treatment
Estimated Study Start Date:	May 1,2022
Estimated Primary Completion Date:	December 31, 2023
Estimated Study Completion Date:	June 1, 2024

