### 3. Study subjects

Subjects with atrial fibrillation and heart failure with different ejection fraction categories are divided to either an anti-arrhythmic drug or cryoballoon catheter pulmonary vein isolation.

(1) Medical treatment group: receive class I or class III AAD to restore or maintain sinus rhythm; Antiarrhythmic drug including Propafenone, Sotalol, Dronedaron and

Amiodarone;

(2) Experimental: cryoballoon ablation group receive cryoballoon ablation to restore sinus rhythm; Pulmonary vein isolation by cryoballoon ablation using Medtronic Arctic Front Advance™ Cardiac CryoAblation Catheters (23mm and 28mm);

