#### **4. Eligibility Criteria**

##### **➤ Inclusion Criteria:**

- (1) Diagnosed with symptomatic paroxysmal or persistent atrial fibrillation: defined as at least two symptomatic episodes in the last six months prior to enrollment.
- (2) At least 18 years old and not older than 80 years old.
- (3) Able and willing to give informed consent.

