##### **➤ Exclusion Criteria:**

- (1) History of AF treatment with class I or III AAD, including sotalol, with the intention to prevent an AF recurrence. However, patients pretreated with above AAD for less than 7 days with the intention to convert an AF episode are allowed;
- (2) Previous left atrial ablation;
- (3) Previous cardiac surgery including prosthetic valves;
- (4) Permanent pacemaker or defibrillator implant;
- (5) Second degree type II or third-degree AV-block or a pattern of left/right bundle branch block;
- (6) History of previous myocardial infarction or percutaneous intervention during the last 3 months;
- (7) Any history of previous transient ischemic attack, prolonged reversible ischemic neurological deficit, and/or stroke;
- (8) Known intracardiac thrombus formation;
- (9) Pulmonary vein stent;
- (10) Known cryoglobulinaemia;
- (11) Active systemic infection;
- (12) Hypertrophic cardiomyopathy;
- (13) Life expectancy is  $\leq 1$  year;
- (14) Reversible cause of atrial fibrillation (eg, hyperthyroidism or alcoholism);
- (15) Abnormal long or short QT intervals, signs of Brugada syndrome, known family history of inherited ion channel disease, and/or arrhythmogenic right ventricular dysplasia;

- 
- (16) Chronic obstructive pulmonary disease with detected pulmonary hypertension and/or any other evidence of significant lung disease;
  - (17) Contraindication for oral anticoagulation;
  - (18) Pregnant women or woman of childbearing potential with inadequate birth control;
  - (19) Women who are breastfeeding;
  - (20) Any significant congenital heart defect corrected or not corrected; however, patent foramen ovale is allowed;
  - (21) Thrombocytosis (platelet count > 600,000 / $\mu$ L) or thrombocytopenia (platelet count < 100,000 / $\mu$ L);
  - (22) Untreated or uncontrolled hyperthyroidism or hypothyroidism;
  - (23) Renal dysfunction with glomerular filtration rate < 60 mL/min;
  - (24) Unstable angina pectoris;
  - (25) Symptomatic carotid stenosis;
  - (26) Myxoma based on laboratory abnormalities;
  - (27) Sarcoidosis;
  - (28) Unwilling to unable to comply with the study procedure and follow-up schedule due to any disease condition;
  - (29) Legal incapacity or evidence that the patient cannot understand the purpose and risks of the study, including inability to comply fully with study procedures and follow-up;
  - (30) Employed by Medtronic, or the department of an investigator, or close-familial relative of an investigator;

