## **7. Statistical analysis**

(1) All statistical analyses were performed using SPSS version 22.0 software (SPSS, Chicago, IL, USA).

(2) All continuous variables were recorded as mean  $\pm$  standard deviation (SD). Categorical variables were presented as numbers or percentages. Between-group comparisons were performed using t-test, Mann–Whitney test, or Chi-square test. Fisher’s exact test was used when the observed value in any of the 2 $\times$ 2 contingency table cells was  $<5$ . Continuous variables were compared among groups using one-way analysis of variance or Kruskal–Wallis test.

(3) The effect of variables on the EF value was analyzed by univariate and multivariate logistic regression analyses. Baseline clinical features, medical history, and clinical and

laboratory parameters on admission were considered as candidate variables in the multivariate analysis.

(4) The association between the EF group and the outcomes was assessed using univariable and multivariable Cox analyses. Variables of relevant clinical interest considered as covariates were included in the multivariable model to identify the predictors for adverse outcomes according to EF category.

(5) A 2-sided p value less than 0.05 was considered as statistically significant.

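### Section 7 specifies no adjusted ablation-versus-drug estimate for a non-randomised comparison; its only Cox model has EF group as the exposure

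*Combined protocol and SAP*

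**What the plan says.** Section 1 states the aim as to "assess the effectiveness and safety of cryoballoon ablation comparing with medical therapy" in patients with atrial fibrillation and heart failure across EF categories. Section 2 gives the allocation as "No-Randomized", with 200 participants. Section 3 says that subjects "are divided to either an anti-arrhythmic drug or cryoballoon catheter pulmonary vein isolation", without an assignment rule, matching or stratification.

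Section 7 then offers:

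- Item (2): "Between-group comparisons were performed using t-test, Mann–Whitney test, or Chi-square test", with Fisher's exact test for small cells and ANOVA or Kruskal–Wallis for several groups. It does not say whether the groups are treatment arms or EF categories.
- Item (3): logistic regression with EF as the dependent variable.
- Item (4): "The association between the EF group and the outcomes was assessed using univariable and multivariable Cox analyses". The covariates are not listed, and their purpose is given as follows: "Variables of relevant clinical interest considered as covariates were included in the multivariable model to identify the predictors for adverse outcomes according to EF category".
- Item (5): two-sided significance at 0.05.

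**The concern.** The question the trial asks is about treatment, and the regression models it plans are about EF. Without randomisation, patients given ablation and patients given drugs may differ in prognosis, so the analysis has to supply whatever comparability it can. Section 7 does not say how.

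Eligibility removes some sources of difference, such as previous stroke, reduced renal function, and (exclusion 1) "History of AF treatment with class I or III AAD, including sotalol" used to prevent recurrence. Others stay open. Inclusion 1 admits both AF types ("Diagnosed with symptomatic paroxysmal or persistent atrial fibrillation"), Section 5.1 spans NYHA classes II to IV, and the study deliberately covers different EF categories.

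If the arms differ on any of these, a crude comparison mixes that difference with the effect of treatment. The plan also leaves the treatment model, its covariates and the EF-by-treatment question to be chosen after the data are seen.

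**Working it through.** **1. Text check.** The documents give no event rate, effect size, allocation ratio or power, so there is no planned figure to reproduce. Setting each item of Section 7 against what the objective needs:

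| Item | Exposure or contrast | Adjusted? | Handles censoring? |
|---|---|---|---|
| (2) two-group and multi-group tests | group, undefined | no | no |
| (3) logistic model | predictors of EF; EF is the outcome, so not a propensity model | not a treatment contrast | no |
| (4) Cox model | EF group | unnamed covariates | yes |

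No item names a treatment hazard ratio, a survival comparison by arm, a propensity score, matching, weighting, or a treatment-by-EF interaction.

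**2. What an unadjusted test can do (illustration; every input assumed).** There is no true treatment effect and one binary prognostic factor. Recurrence is 50% with the factor and 30% without. The arm recurrence rate is 0.30 + 0.20 × prevalence; for example, 0.30 + 0.20 × 0.70 = 0.44 and 0.30 + 0.20 × 0.30 = 0.36. The test is z = (p̂₁ − p̂₂)/√[p̄(1 − p̄)(1/n₁ + 1/n₂)], rejecting when |z| > 1.96, with binomial probabilities summed exactly over all outcomes.

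| Prevalence by arm | Recurrence by arm | Rejects, 100:100 | Rejects, 140:60 (larger arm has higher prevalence) |
|---|---|---|---|
| 50/50 | 40/40% | 5.1% | 5.0% |
| 55/45 | 41/39% | 6.1% | 5.7% |
| 60/40 | 42/38% | 9.1% | 8.1% |
| 65/35 | 43/37% | 14.2% | 12.2% |
| 70/30 | 44/36% | 21.5% | 18.0% |

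**3. The same patterns in a Cox model.** This simulation used 10,000 trials per pattern, exponential times, censoring at one year, 100:100 and no treatment effect.

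| Prevalence by arm | Treatment alone: rejects (HR) | Adjusted for the factor: rejects (HR) | SE of log HR, crude → adjusted |
|---|---|---|---|
| 50/50 | 5.4% (1.00) | 5.3% (1.00) | 0.2253 → 0.2260 |
| 55/45 | 5.8% (1.07) | 5.0% (1.00) | 0.2252 → 0.2270 |
| 60/40 | 9.0% (1.14) | 4.7% (1.00) | 0.2255 → 0.2306 |
| 65/35 | 14.1% (1.22) | 5.1% (1.00) | 0.2259 → 0.2369 |
| 70/30 | 20.8% (1.30) | 4.5% (1.00) | 0.2264 → 0.2467 |

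The cost in standard error runs from 0.2260/0.2253 = 1.003 to 0.2467/0.2264 = 1.09.

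**4. Precision of the model that is missing.** Assume equal arms, three equal EF categories and 30% to 50% recurrence, so E = 60 to 100 events if all 200 are followed. The 95% interval is the HR times or divided by exp(1.96√v).

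| Estimate | v | E = 60 to 100 | E = 30 to 50 (half followed, assumed) |
|---|---|---|---|
| Overall HR | 4/E | 1.66 to 1.48 | 2.05 to 1.74 |
| HR in one EF category | 4/(E/3) | 2.40 to 1.97 | 3.45 to 2.61 |
| Ratio of two EF-specific HRs | 8/(E/3) | 3.45 to 2.61 | 5.77 to 3.89 |

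**5. Events per parameter.** Seven parameters (treatment, two EF terms, age, sex, AF type, NYHA II versus III–IV) give 60/7 = 8.6 to 100/7 = 14.3, or 30/7 = 4.3 to 50/7 = 7.1. With two interaction terms (nine parameters) this becomes 6.7 to 11.1, or 3.3 to 5.6. For death or HF hospitalisation, an assumed 5% to 10% of 200 is 10 to 20 events, or 1.4 to 2.9 per parameter with seven. Treatment plus one propensity-score term gives 5 to 10.

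**The case against.** The strongest reply is that the plan does not rule adjustment out. Item (4) is multivariable, and treatment may be among its unnamed covariates. Item (2) can be read as comparing the two arms, since Sections 3 and 5 use the word group for them. Section 6 also defines the primary outcome as success at 12 months, and a chi-square test can analyse that binary form when status is known for everyone. All of this is fair. But a covariate that may be omitted is not a specified treatment analysis, and a chi-square test on the binary outcome is still unadjusted.

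The illustration also has limits that stand. At 55/45 the rejection rate is 6.1%, close to nominal, and 21.5% needs a 40-point imbalance in a factor that moves recurrence by 20 points. The adjusted results are a best case, with one confounder, perfectly measured and included. They say nothing about unmeasured reasons for choosing ablation.

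Halving events in both arms is one assumption among several. Section 5.2 describes the reconsented subset only after ablation, alongside telephone interviews and symptom-driven visits. Halving only the ablation arm gives 30 + 15 = 45 to 50 + 25 = 75 events, an overall interval factor of 1.86 to 1.62 (v = 1/30 + 1/15 to 1/50 + 1/25), and 45/7 = 6.4 to 75/7 = 10.7 events per parameter.

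Finally, the interaction will be imprecise under any of these scenarios. That is a reason to label it so; the objective still asks for it.

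**Conclusion.** The concern holds and must be fixed. This is a reading of the text and does not depend on the illustration: the plan specifies no treatment-effect model, no confounder adjustment for the ablation-versus-drug contrast, and no estimate of how that contrast varies with EF. The item (4) EF analysis answers part of the objective, but not its main comparison.

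The documents do not show whether the arms differ or in which direction any bias would run. Under the stated assumptions, moderate to large imbalance in one measured factor takes a nominal 5% test to between about 9% and 21%, and adjusting for that factor restores it at a cost of up to 9% in standard error.

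**What to change.** Before outcomes are examined by arm, add to item (4):

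- A primary Cox model for time to first recurrence after the 3-month period, with treatment as the exposure. State how it relates to the binary 12-month definition in Section 6.
- A short fixed list of baseline confounders available in both arms, for example age, sex, AF type, NYHA class and EF entered once, with the EF categories defined.
- EF-specific treatment hazard ratios and a treatment-by-EF interaction, labelled imprecise at 200 patients.
- A fallback if recurrences are few: treatment plus one propensity-score term, which gives 30/2 = 15 to 50/2 = 25 events per parameter at 30 to 50 events.

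Keep the EF-group analysis as secondary and label crude item (2) comparisons as supportive. Use the same baseline adjustment for quality-of-life change. For all-cause mortality, HF hospitalisation and their composite, adjust only as far as events allow (one propensity term or weighting, otherwise descriptive). Report procedural complications descriptively in the ablation arm.

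The cost is SAP wording, slightly wider intervals and few events per parameter. It depends on a condition the documents do not confirm, that covariates and follow-up exist in both arms. Section 5.1 mentions echocardiography without listing measurements, whereas Section 5.2 names LVEF, although the EF analyses presuppose it in everyone. Scheduled visits are described only after ablation and for a subset. A model cannot repair missing drug-arm data, and residual confounding must be acknowledged in the report.

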## **6. Outcome Measures**

➤ **Primary Outcome Measures:**

(1) Treatment success at one year

Treatment success at 12 months after antiarrhythmic drug (AAD) initiation or ablation utilizing cryoballoon catheter measured by freedom from AF recurrence following a 3-month period after the index ablation or AAD initiation.

The primary outcome was time to first documented recurrence of symptomatic or asymptomatic atrial tachyarrhythmia (AF, atrial flutter, or atrial tachycardia)

(2) Rate of serious adverse events

Rate of complications and adverse events occurred during cryoballoon ablation and postoperative follow-up, including procedure-related complications such as bleeding, phrenic nerve palsy (PNP), cerebral embolism, pericardial effusion/tamponade, atriopharyngeal fistula, and all-cause mortality, re-hospitalization for HF, and the composite event of all-cause mortality or HF hospitalization.

➤ **Secondary Outcome Measures**

(1) Quality of life changes at 12 months measured by AF Quality of Life Survey (AFEQT)

The improvement in quality of life between baseline and 12 months after the index ablation procedure or AAD measured by AFEQT is evaluated.

(2) Quality of life changes at 12 months measured by 12-Item Short Form Survey (SF-12)

The improvement in quality of life between baseline and 12 months after the index ablation procedure or AAD measured by SF-12 is evaluated.

(3) Arrhythmia recurrence during blanking period (Time Frame: 3 months)

Atrial tachycardia recurrence rate during the blanking period is evaluated.

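### The only Cox analysis takes EF group as its exposure and names neither treatment nor a treatment-by-EF term, so it cannot show whether the ablation effect differs by EF category

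*Combined protocol and SAP*

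**What the plan says.** Section 1 gives the aim as assessing "effectiveness and safety of cryoballoon ablation comparing with medical therapy in patients with atrial fibrillation and heart failure with different ejection fraction categories". Section 3 repeats the EF wording for the patients who are assigned to drug or ablation. Section 2 plans "200 participants" with allocation given as "No-Randomized". It gives no ratio between arms and no basis for the sample size. No section states how many EF categories there are or where they are cut.

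In section 6, the first primary outcome is described as a time to event: "The primary outcome was time to first documented recurrence of symptomatic or asymptomatic atrial tachyarrhythmia".

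Section 7 offers three kinds of analysis:

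- Item (2) lists one-factor comparisons (t-test, Mann–Whitney, chi-square or Fisher, ANOVA, Kruskal–Wallis) between groups. It does not say whether a group is a treatment arm or an EF category.
- Item (3) uses logistic regression with EF itself as the dependent variable.
- Item (4) is the Cox analysis: "The association between the EF group and the outcomes was assessed using univariable and multivariable Cox analyses". Its multivariable version adds unlisted covariates of clinical interest "to identify the predictors for adverse outcomes according to EF category".

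**The concern.** What distinguishes this trial from a general ablation-versus-drug comparison is the spread of EF categories. A reader will expect it to say whether ablation does better or worse in some categories than in others. That is a question of effect modification, and it needs an analysis in which treatment and EF category appear together with their product.

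Item (4) answers a different question: whether patients in one EF category have more events than patients in another. A hazard ratio for EF group is prognostic and carries no information on the ablation effect within a category. If treatment entered as one of the unlisted covariates, the model would give a single average treatment effect and still nothing by category.

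The gap leaves room for an informal substitute: testing treatment separately in each category and comparing the verdicts. A significant result in one category and a non-significant one in another is not evidence that the effects differ. The plan has no rule against reading it that way; item (5) gives only the two-sided 0.05 threshold.

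**Working it through.** **1. Which analysis crosses treatment with EF?** Item (2): one factor at a time. Item (3): EF is the dependent variable. Item (4): EF is the exposure and treatment is not named. None crosses them.

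**2. Inputs.** From the documents: N = 200, two-sided alpha 0.05. There is no planned power, effect size or event rate, so there is no design figure to reproduce. Assumed: 100 per arm, two or three EF categories, and the same true effect in every category.

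**3. How often would separate tests give mixed verdicts under one common effect?** Let p₁, …, p_k be the power of the Pearson chi-square test in each category, found by exact binomial enumeration. Then

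P(mixed) = 1 − Πpᵢ − Π(1 − pᵢ).

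Three categories have 33, 33 and 34 patients per arm; two categories have 50 per arm each.

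Example, success 50% v 70%:
- Pooled power, 100 v 100: 0.832.
- Three categories: power 0.413, 0.413, 0.403. P(all) = 0.413 × 0.413 × 0.403 = 0.069. P(none) = 0.587 × 0.587 × 0.597 = 0.206. P(mixed) = 1 − 0.069 − 0.206 ≈ 0.73.
- Two categories: power 0.546 each. P(mixed) = 2 × 0.546 × 0.454 = 0.496.

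| Success, drug v ablation | Mixed, three categories | Mixed, two categories |
|---|---|---|
| 50 v 65% | 57% | 45% |
| 50 v 70% | 73% | 50% |
| 45 v 70% | 73% | 39% |
| 45 v 75% | 58% | 21% |

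Outside these moderate effects, three categories give 16% (no effect, 50 v 50%), 37% (50 v 60%), 17% (40 v 80%) and 8% (30 v 75%). With two equal categories, 2p(1 − p) cannot exceed 50% whatever the effect.

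**4. Cross-check on the hazard scale.** By Schoenfeld's formula, power = Φ(√(D/4) × |ln HR| − 1.96). Take control recurrence 50% and HR 0.5. Ablation recurrence is 1 − 0.5^0.5 = 0.29, so D = 100 × (0.50 + 0.29) ≈ 79 events. Overall power is 87%. In each of three equal categories it is 43%, and P(mixed) = 1 − 0.43³ − 0.57³ ≈ 0.74. With two equal categories P(mixed) is about 48–49%.

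**5. Precision within one category.** With 33 per arm and success 50% v 70%, the 95% half-width of the difference is 1.96 × √(0.25/33 + 0.21/33) = 0.231, about 23 percentage points.

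**6. Power of the interaction test.** For two equal categories the variance of the difference in log hazard ratios is 16/D. For a ratio of hazard ratios of 0.5 and D = 80, the standard error is √(16/80) = 0.447 and power is Φ(0.693/0.447 − 1.96) = 34%. With D = 120 it is 48%. For three equal categories (2 degrees of freedom, middle category halfway on the log scale) power is 19% and 26%. For 80% power with two categories, D = 16 × (1.96 + 0.84)² / 0.693² ≈ 262 events, more than the 200 patients enrolled.

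**The case against.** The strongest reply is that the objective never promises a test of effect differences. The words "comparing with medical therapy in patients with atrial fibrillation and heart failure with different ejection fraction categories" can simply describe the population, and no hypothesis or outcome in section 6 mentions effect modification. This stands in part: the gap is against an implied aim, not a declared primary analysis. It does not rescue item (4). If EF only describes the population, the plan's one time-to-event model still does not name the treatment comparison.

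A second reply is that the unlisted covariates may include treatment. They may, but a main effect gives one average hazard ratio.

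A third is that an interaction test at this size has little power. Step 6 confirms it. That argues for calling the analysis exploratory, not for leaving the question to an unplanned comparison of p-values.

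A reader might go further and infer that the trial will probably report a false difference between EF categories. The documents do not support that. Section 7 nowhere says that treatment will be tested within each category or that such verdicts will be compared. The phrase "to identify the predictors for adverse outcomes according to EF category" fits EF as a factor in one model as well as it fits separate models. The number of categories is not given, and the chance of a mixed pattern is at or below one half with two equal categories, or with three when the effect is absent, small or very large. A mixed pattern also becomes a false claim only if someone reads it as one.

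**Conclusion.** The omission is real and can be read directly from section 7: no treatment term is named in the Cox analysis and no treatment-by-EF term appears anywhere. Followed as written, the plan yields prognosis by EF and cannot say whether the ablation effect differs by EF category. This part needs no assumptions.

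The size of the subgroup hazard is conditional. It applies only if effects are judged by separate within-category p-values, and the 57–73% and 21–50% ranges rest on the arm split, category counts and success rates assumed in the working.

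This should be fixed. It falls short of a fatal flaw because the aim is implied and the test that would answer it is underpowered.

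**What to change.** 1. Define the EF categories: their number and cut-points.
2. In item (4), fit one Cox model for primary outcome (1) in all patients, with treatment, EF category, treatment × EF category and a prespecified list of baseline confounders. Allocation is not randomized, so without adequate adjustment the interaction can be biased and its nominal 5% false-claim rate is not assured.
3. Report the treatment hazard ratio with its 95% confidence interval in each EF category from that model, together with the interaction p-value.
4. State that a difference between categories will be claimed only from the interaction test, never from comparing separate p-values.
5. Fit the same model for the composite of death or HF hospitalisation, and label both interaction analyses exploratory.

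The cost is a short addition to section 7. EF and baseline clinical characteristics are already due to be recorded, so no new data should be needed, provided the chosen confounders are among them. The drawback is low power at 200 patients: intervals by category will be wide, and the likely conclusion is that no difference was shown, which must not be reported as proof of a uniform effect.
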